8.2.4 Serious Adverse Events and Deaths

SAEs, and SAEs by relationship will be presented as described for AEs in Section [8.2.2](#).

A listing of patients who experienced SAEs will also be provided. A separate listing of deaths will be included.

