5.6 UCB Pharmacovigilance Reporting

Adverse events collected from the registry that occur within 70 days of last Cimzia dose will be included in UCB's safety database and reported to the FDA as per regulatory reporting guidelines. Registry cases of malignancy, death, and pregnancy will be included in UCB's safety database and reviewed and evaluated for FDA reporting even if the event occurs after 70 days of last Cimzia dose. Any reports received prior to start of the registry and after completion of the study will be evaluated and reported as per standard UCB pharmacovigilance plans for spontaneous reporting.

Figure 5–1: Event reporting process

AE=adverse event; EDC=electronic data capture; SAE=serious adverse event

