6.4.2 Secondary Analyses

Descriptive statistics on the Investigator's assessment of disease at study entry will be presented. Disease severity, measured by Investigator's and patient's assessment, will be used to quantify the potential influence of disease severity on the safety profile. Demographics and baseline patient characteristics, including medical history, CD history, physical examination findings (if available), vital signs (if available), the HBI score, patient's assessment, and reasons for treatment and study discontinuation will be summarized. Concomitant medications will be presented following the World Health Organisation Drug (WHO Drug)

classification. Characteristics of treatment with Cimzia or other medication such as planned treatment duration and actual duration of therapy will be tabulated. A stratified analysis by cumulative Cimzia exposure may also be performed for malignancy events to identify potential patterns in long-term use of Cimzia.

All AEs will be summarized descriptively by MedDRA Primary System Organ Class and Preferred Term (latest version at each interim analysis). Each interim analysis will indicate the MedDRA version that was utilized. Additional tables will summarize those AEs by severity and relationship to study drug as well as separate tables for AEs leading to withdrawal from the study, SAEs and deaths.

Further details on all analyses will be provided in the SAP.

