8.2.2 Adverse Events

Any event reported by the investigator or found in the drug safety database excerpt is considered an adverse event. Investigator and drug safety AEs have been reconciled by the study physician to avoid over reporting.

When an AE is considered serious in either source, it is treated as serious in the analysis and the related coding data is used.

Events reported in the patient survey are not considered confirmed AEs and are excluded from the analysis.

AE tabulations will be done using malignancy rules (for malignancies) separately using acute event rules (all AEs) unless otherwise specified.

A summary of study-emergent AEs, including the number of events reported, the number and percentage of patients reporting at least one AE, the number and percentage of patients reporting at least one AE of Interest, the number and percentage of patients with at least one serious AE (SAE), and the number and percentage of deaths will be presented. In addition, the number and percentage of patients reporting at least one study-emergent treatment-related AE, the number and percentage of patients reporting at least one study-emergent treatment-related AE of Interest, and the number and percentage of patients with at least one study-emergent treatment-related SAE will also be reported. AE summaries will be produced on the enrolled cohort as well as the malignancy/acute event rules.

Study-emergent AEs are those which first occur or increase in relationship to treatment after the first dose of any CD drug following enrollment.

A breakdown of the number and percentage of patients reporting each AE as well as the number of AEs, categorized by SOC, HLT, and PT coded according to MedDRA, will be presented. Note that patients are only counted once within each SOC, HLT, or PT. Uncoded AEs will be summarized in unknown SOC, HLT and PT. This will be produced for the enrolled cohort as well as both the malignancy and acute event rules.

A further tabulation of these data, broken down by relationship to treatment, will be presented. Patients with multiple events within a particular body system or preferred term will be counted under the category of their most drug-related event within that SOC, HLT or PT. Relationship to treatment is categorized as related or not related as collected on the eCRF.

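### Deaths are planned only as a number and percentage plus a listing, with no mortality rate or interval by treatment; separately, two AE tables in Protocol 6.4.2 have no counterpart in the SAP

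*SAP*

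**What the plan says.** **Deaths.** SAP 8.2.4 covers serious adverse events and deaths. SAEs get tables, overall and by relationship, and a listing. For deaths the section says: "A separate listing of deaths will be included". SAP 8.2.2 describes an overview table in which "the number and percentage of patients with at least one serious AE (SAE), and the number and percentage of deaths will be presented". On grouping it adds: "AE summaries will be produced on the enrolled cohort as well as the malignancy/acute event rules".

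**Rates and contrasts.** SAP 8.1.3 (time-to-event) and 8.1.4 (incidence rates per 100 patient-years, Poisson 95% limits, regression) are written for adverse events of interest. Death is not in the lists in SAP 2.2.1 and section 8, and not among the rows of Table 8.1.

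**Other AE tables.** Protocol 6.4.2 says: "Additional tables will summarize those AEs by severity and relationship to study drug", and also commits to "separate tables for AEs leading to withdrawal from the study, SAEs and deaths". SAP 8.2.2 keeps the breakdown by relationship. No SAP section specifies a severity breakdown or a table of AEs leading to withdrawal. The nearest item is the summary of reasons for discontinuation in SAP 5.1.

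**The concern.** The registry's one objective, in Protocol section 3 and SAP 2.1.1, is to measure safety outcomes on Cimzia against those on other regimens. All-cause death is the safety outcome least open to misclassification. As the SAP stands, the final report would give a percentage of deaths per group and a list of cases, with no planned rate or measure of uncertainty for either group.

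A percentage needs a common follow-up time and a fixed set of patients per group, and this design has neither. SAP 3.6 expects patients to change treatment and divides their time among groups. Follow-up differs with enrollment date and drop-out.

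The plan already does more for lesser items. Study discontinuation gets Kaplan-Meier estimates and a hazard ratio in SAP 5.1. Hepatic events, which the SAP says are not officially of interest, have a row in Table 8.1.

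The missing withdrawal table is a smaller matter, but it bears on whether patients leave the registry because of adverse events. At the plan's own 8% annual drop-out, 1 − 0.92^8 = 49% would have left by year 8.

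**Working it through.** **1. Protocol 6.4.2 against the SAP text**

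| Protocol 6.4.2 item | SAP counterpart |
|---|---|
| AEs by relationship | Yes, 8.2.2 |
| AEs by severity | None |
| AEs leading to withdrawal | None; 5.1 gives discontinuation reasons, which is not an AE table |
| SAEs | Yes, 8.2.4 |
| Deaths, separate table | Number and percentage in the 8.2.2 overview, plus the 8.2.4 listing |

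Protocol 6.4.2 promises descriptive tables and names no mortality rate. The missing rate therefore has its own cause: 8.1.3 and 8.1.4 are limited to adverse events of interest. None of the amendment rationales in SAP section 12 mentions dropping the severity or withdrawal tables.

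**2. Why a percentage does not compare**

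Under the malignancy rule (SAP 3.2.1.1), a comparator patient who starts Cimzia contributes time first to Comparator and then to Cimzia. Under the acute rule (3.2.1.2 and 3.6), one patient can contribute to Cimzia, Comparator, Overlap and Gap. That patient can be in several denominators but dies in one group only. The percentage then depends on how long each group's time lasts as well as on the death rate. By enrollment cohort the denominators are fixed, but follow-up length still enters.

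**3. Would there be enough deaths for a rate?**

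The documents give no mortality figure, so there is nothing to reproduce.

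Inputs from the documents:
- 3045 patients (1371 Cimzia, 1674 comparator) enrolled as of March 2017, with follow-up capped at 8 years (Protocol 6.3).
- 8% annual drop-out, which already includes death (Protocol 6.3, SAP 2.4).
- Study end on 28 August 2020 (SAP 2.3).

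Assumed: a death rate of 0.5 per 100 patient-years, range 0.2 to 1.0.

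The shortest possible follow-up for a patient enrolled by the end of March 2017 is about 3.4 years. Mean observed time is (1 − 0.92^T) / (−ln 0.92), with −ln 0.92 = 0.0834.

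- T = 3.4 for everyone: (1 − 0.753) / 0.0834 = 2.96 years; × 3045 ≈ 9,000 patient-years.
- T = 8 for everyone: (1 − 0.513) / 0.0834 = 5.84 years; × 3045 ≈ 17,800 patient-years.

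These are outer bounds. Expected total deaths (rate × patient-years):

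| Assumed rate per 100 p-y | 9,000 p-y | 17,800 p-y |
|---|---|---|
| 0.2 | 18 | 36 |
| 0.5 | 45 | 89 |
| 1.0 | 90 | 178 |

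For the Cimzia cohort at 0.5 per 100 patient-years, with exact Poisson limits:
- Upper bound: 1371 × 5.84 ≈ 8,000 p-y and 40 deaths. Limits on the count are 28.6 and 54.5, so the rate has 95% CI 0.36 to 0.68.
- Lower bound: 1371 × 2.96 ≈ 4,060 p-y and 20 deaths. Limits are 12.2 and 30.9, so the CI is 0.30 to 0.76.

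At the sparsest corner (0.2 per 100, 4,060 p-y) there are about 8 deaths, with CI 0.09 to 0.39. That is wide but still reportable.

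**The case against.** The strongest reply is that the SAP does summarise deaths. SAP 8.2.2 tabulates them by group, and because death is a seriousness criterion, fatal events also enter the SAE tables. Death is not an endpoint in Protocol 6.1.1 or SAP 2.2.1, and Protocol 6.4.2 promises no mortality rate. A reader could divide the death counts by the patient-years that SAP 5.1 and 8.2.1 report. All of this stands. A reader who sees only 8.2.4 might infer that the SAP leaves deaths as a listing alone, or that it breaks a promise of a mortality rate. The documents support neither reading. What remains is that a rate worked out by hand has no planned interval or contrast, while the percentage that is planned does not compare the groups.

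Three further inferences should be avoided:
- Protocol 5.6 keeps death reviewable "even if the event occurs after 70 days of last Cimzia dose". That governs the sponsor's safety database and reporting to the FDA. It is not an attribution rule for analysis and does not require the ever-Cimzia rule for deaths.
- At 0.5 deaths per 100 patient-years, the crude percentage is 1 − exp(−0.005 × 3.4) = 1.7% at 3.4 years and 1 − exp(−0.005 × 8) = 3.9% at 8 years, a 2.3-fold ratio. This compares two follow-up lengths, not Cimzia with comparator. With 8% drop-out, mean follow-up differs by 5.84 / 2.96 = 2.0-fold. The documents give no evidence that the cohorts differ in follow-up, and recruitment was to be balanced over time.
- 17,800 patient-years is an upper bound, since it gives everyone a full 8 years.

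On the other tables, SAP 5.1 analyses discontinuation in some detail, which partly addresses differential drop-out. The current protocol's data collection lists do not name AE severity, so its capture is not shown. The eCRF and table shells are not among the documents, and the shells may contain tables that the text omits.

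**Conclusion.** The point holds in two separate parts.

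First, no mortality rate per patient-year, interval or contrast is planned by treatment, and the planned percentage cannot be compared between groups when patients switch and follow-up is unequal. This falls short of the registry's comparative safety objective, but it does not breach Protocol 6.4.2. The expected yield, about 45 to 89 deaths at the central assumed rate and 18 to 178 across the range, supports a rate with an interval. Those counts rest on the assumed death rates, the plan's 8% drop-out and the March 2017 enrollment of 3045. SAP 2.4 gives 3076 at final analysis, which changes them by about 1%.

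Second, the SAP text has no counterpart to the severity and withdrawal-AE tables of Protocol 6.4.2. That mismatch should be reconciled.

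Both parts are worth correcting. Neither undermines the malignancy analysis.

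**What to change.** In SAP 8.2.4, or as a row in Table 8.1, add all-cause death with:
- number of deaths and patient-years to death or last follow-up;
- rate per 100 patient-years with the Poisson 95% CI of 8.1.4;
- a descriptive rate ratio with 95% CI.

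Present it by enrollment cohort and by the ever-Cimzia rule of 3.2.1.1, and keep the listing. State which rule applies to the death row in the 8.2.2 overview: one sentence there ties the malignancy rule to malignancies, and another applies both rules to AE summaries.

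Add a table of AEs leading to withdrawal from the study. Add the table of AEs by severity if the eCRF captures AE severity. If it does not, say so in the SAP and reconcile it with Protocol 6.4.2.

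The cost is SAP wording and two or three tables built on existing groupings and the method already in 8.1.4. The only downside is a little more programming.

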9 PHARMACOKINETICS AND PHARMACODYNAMICS

Not applicable.

This document cannot be used to support any marketing authorization application and any extensions or variations thereof.
REDACTED COPY

11 APPENDICES

11.1 Appendix 1 – Treatment Allocation of Malignancies and Acute Adverse Events

Assumptions:

- Treatment periods described in the dosing column have the drug half-life added to the end of each treatment.
- Overlap is when comparator and Cimzia treatment periods overlap. The overlap can occur during the extended treatment for the drug half-life.
- Abbreviations; IC=Informed Consent Date, EoS= End of Study Date
- Gap and Overlap are not possible treatment groups for Malignancy Time at Risk as per SAP section 3.2.1.1 “Person-time at risk calculations for malignancy”. Overlap would be considered Cimzia and Gap would be assigned to the prior treatment.
- The dosing prior to IC only has an impact on malignancy time at risk. If a subject has no Cimzia dosing prior to IC it is considered to have had Comparator dosing prior to IC regardless of what is recorded in the dosing information.

#	Dosing prior to IC	Dosing during study (IC onwards)	Adverse Event	Treatment AE assigned to	Malignancy Time at Risk		Other AE Time at Risk			
					Cimzia	Comparator	Cimzia	Comparator	Gap	Overlap
1a	No Cimzia	Comparator > Cimzia > Comparator	None	N/A	Start of Cimzia to EoS	IC to Start of Cimzia	Start of Cimzia to Start of Second Period of Comparator	(IC to Start of Cimzia) plus (Start of Second Period of Comparator to EoS)	None	None
1b	Cimzia	Comparator > Cimzia > Comparator	None	N/A	IC to EoS	None	Start of Cimzia to Start of Second Period of Comparator	(IC to Start of Cimzia) plus (Start of Second Period of Comparator to EoS)	None	None

#	Dosing prior to IC	Dosing during study (IC onwards)	Adverse Event	Treatment AE assigned to	Malignancy Time at Risk		Other AE Time at Risk			
					Cimzia	Comparator	Cimzia	Comparator	Gap	Overlap
2a	No Cimzia	Comparator > Cimzia > Comparator	Malignancy during second period of Comparator	Cimzia	Start of Cimzia to Malignancy Start Date	IC to Start of Cimzia	Start of Cimzia to Start of Second Period of Comparator	(IC to Start of Cimzia) plus (Start of Second Period of Comparator to EoS)	None	None
2b	Cimzia	Comparator > Cimzia > Comparator	Malignancy during second period of Comparator	Cimzia	IC to Malignancy Start Date	None	Start of Cimzia to Start of Second Period of Comparator	(IC to Start of Cimzia) plus (Start of Second Period of Comparator to EoS)	None	None
3a	No Cimzia	Comparator > Cimzia > Comparator	Malignancy during first period of Comparator	Comparator	None	IC to Malignancy Start Date	Start of Cimzia to Start of Second Period of Comparator	(IC to Start of Cimzia) plus (Start of Second Period of Comparator to EoS)	None	None
3b	Cimzia	Comparator > Cimzia > Comparator	Malignancy during first period of Comparator	Cimzia	IC to Malignancy Start Date	None	Start of Cimzia to Start of Second Period of Comparator	(IC to Start of Cimzia) plus (Start of Second Period of Comparator to EoS)	None	None

#	Dosing prior to IC	Dosing during study (IC onwards)	Adverse Event	Treatment AE assigned to	Malignancy Time at Risk		Other AE Time at Risk			
					Cimzia	Comparator	Cimzia	Comparator	Gap	Overlap
4a	No Cimzia	Comparator > Cimzia > Comparator	Other AE during second period of Comparator	Comparator	Start of Cimzia to EoS	IC to Start of Cimzia	Start of Cimzia to Start of Second Period of Comparator	(IC to Start of Cimzia) plus (Start of Second Period of Comparator to Other AE start date)	None	None
4b	Cimzia	Comparator > Cimzia > Comparator	Other AE during second period of Comparator	Comparator	IC to EoS	None	Start of Cimzia to Start of Second Period of Comparator	(IC to Start of Cimzia) plus (Start of Second Period of Comparator to Other AE start date)	None	None
5a	No Cimzia	Comparator > Overlap > Cimzia	Malignancy during Overlap	Cimzia	Start of Overlap to Malignancy Start Date	IC to Start of Overlap	Start of Cimzia to EoS	IC to Start of Overlap	None	Start of Overlap to Start of Cimzia
5b	Cimzia	Comparator > Overlap > Cimzia	Malignancy during Overlap	Cimzia	IC to Malignancy Start Date	None	Start of Cimzia to EoS	IC to Start of Overlap	None	Start of Overlap to Start of Cimzia

#	Dosing prior to IC	Dosing during study (IC onwards)	Adverse Event	Treatment AE assigned to	Malignancy Time at Risk		Other AE Time at Risk			
					Cimzia	Comparator	Cimzia	Comparator	Gap	Overlap
6a	No Cimzia	Comparator > Overlap > Cimzia	Other AE during Overlap	Overlap	Start of Overlap to EoS	IC to Start of Overlap	None	IC to Start of Overlap	None	Start of Overlap to Other AE start date
6b	Cimzia	Comparator > Overlap > Cimzia	Other AE during Overlap	Overlap	IC to EoS	None	None	IC to Start of Overlap	None	Start of Overlap to Other AE start date
7a	No Cimzia	Comparator > Overlap > Cimzia	None	N/A	Start of Overlap to EoS	IC to Start of Overlap	Start of Cimzia to EoS	IC to Start of Overlap	None	Start of Overlap to Start of Cimzia
7b	Cimzia	Comparator > Overlap > Cimzia	None	N/A	IC to EoS	None	Start of Cimzia to EoS	IC to Start of Overlap	None	Start of Overlap to Start of Cimzia
8a	Cimzia	Comparator > Gap > Cimzia	Malignancy during Cimzia	Cimzia	IC to Malignancy Start Date	None	Start of Cimzia to EoS	IC to End of Comparator	Start of Gap to End of Gap	None
8b	No Cimzia	Comparator > Gap > Cimzia	Malignancy during Cimzia	Cimzia	Start of Cimzia to Malignancy Start Date	IC to End of Gap	Start of Cimzia to EoS	IC to End of Comparator	Start of Gap to End of Gap	None

#	Dosing prior to IC	Dosing during study (IC onwards)	Adverse Event	Treatment AE assigned to	Malignancy Time at Risk		Other AE Time at Risk			
					Cimzia	Comparator	Cimzia	Comparator	Gap	Overlap
9	No Cimzia or Cimzia	Cimzia > Gap > Comparator	Malignancy during Comparator	Cimzia	Start of Cimzia to Malignancy Start Date	None	Start of Cimzia to End of Cimzia	Start of Comparator to End of Comparator	Start of Gap to End of Gap	None
10	No Cimzia or Cimzia	Cimzia > Gap > Comparator	Malignancy during Gap	Cimzia	Start of Cimzia to Malignancy Start Date	None	Start of Cimzia to End of Cimzia	Start of Comparator to EoS	Start of Gap to End of Gap	None
11	No Cimzia or Cimzia	Cimzia > Gap > Comparator	Other AE during Gap	Gap	Start of Cimzia to EoS	None	Start of Cimzia to End of Cimzia	None	Start of Gap to Other AE start date	None
12	No Cimzia or Cimzia	Cimzia > Gap > Comparator	None	N/A	Start of Cimzia to EoS	None	Start of Cimzia to End of Cimzia	Start of Comparator to End of Comparator	Start of Gap to End of Gap	None
13	No Cimzia or Cimzia	Cimzia > Comparator	Malignancy during Comparator and Other AE during Comparator	Malignancy (Cimzia), Other AE (Comparator)	Start of Cimzia to Malignancy Start Date	None	Start of Cimzia to End of Cimzia	Start of Comparator to Other AE start date	None	None

#	Dosing prior to IC	Dosing during study (IC onwards)	Adverse Event	Treatment AE assigned to	Malignancy Time at Risk		Other AE Time at Risk			
					Cimzia	Comparator	Cimzia	Comparator	Gap	Overlap
14a	No Cimzia	Comparator > Gap > Cimzia	Malignancy during Gap	Comparator	None	Start of Comparator to Malignancy Start Date	Start of Cimzia to End of Cimzia	Start of Comparator to End of Comparator	Start of Gap to End of Gap	None
14b	Cimzia	Comparator > Gap > Cimzia	Malignancy during Gap	Cimzia	IC to Malignancy Start Date	None	Start of Cimzia to End of Cimzia	Start of Comparator to End of Comparator	Start of Gap to End of Gap	None
15a	No Cimzia	Comparator > Gap > Cimzia	First Malignancy during Gap and Second Malignancy during Cimzia	Comparator	None	Start of Comparator to First Malignancy Start Date	Start of Cimzia to End of Cimzia	Start of Comparator to End of Comparator	Start of Gap to End of Gap	None
15b	Cimzia	Comparator > Gap > Cimzia	First Malignancy during Gap and Second Malignancy during Cimzia	Cimzia	IC to Malignancy Start Date	None	Start of Cimzia to End of Cimzia	Start of Comparator to End of Comparator	Start of Gap to End of Gap	None
16a	No Cimzia	Gap > Cimzia	Malignancy during Gap	Comparator	None	IC to Malignancy Start Date	Start of Cimzia to End of Cimzia	None	IC to End of Gap	None

#	Dosing prior to IC	Dosing during study (IC onwards)	Adverse Event	Treatment AE assigned to	Malignancy Time at Risk		Other AE Time at Risk			
					Cimzia	Comparator	Cimzia	Comparator	Gap	Overlap
16b	Cimzia	Gap > Cimzia	Malignancy during Gap	Cimzia	IC to Malignancy Start Date	None	Start of Cimzia to End of Cimzia	None	IC to End of Gap	None
17a	No Cimzia	Gap > Comparator	Malignancy during Gap	Comparator	None	IC to Malignancy Start Date	None	Start of Comparator to End of Comparator	IC to End of Gap	None
17b	Cimzia	Gap > Comparator	Malignancy during Gap	Cimzia	IC to Malignancy Start Date	None	None	Start of Comparator to End of Comparator	IC to End of Gap	None
18a	No Cimzia	Gap > Cimzia	Other AE during Gap	Gap	Start of Cimzia to EoS	IC to Start of Cimzia	None	None	IC to Other AE start date	None
18b	Cimzia	Gap > Cimzia	Other AE during Gap	Gap	IC to EoS	None	None	None	IC to Other AE start date	None
19a	No Cimzia	Gap only i.e. no evidence of Comparator or Cimzia dosing	Malignancy during Gap	Comparator	None	IC to Malignancy Start Date	None	None	IC to EoS	None

#	Dosing prior to IC	Dosing during study (IC onwards)	Adverse Event	Treatment AE assigned to	Malignancy Time at Risk		Other AE Time at Risk			
					Cimzia	Comparator	Cimzia	Comparator	Gap	Overlap
19b	Cimzia	Gap only i.e. no evidence of Comparator or Cimzia dosing	Malignancy during Gap	Cimzia	IC to Malignancy Start Date	None	None	None	IC to EoS	None
20a	No Cimzia	Gap only i.e. no evidence of Comparator or Cimzia dosing	Other AE during Gap	Gap	None	IC to EoS	None	None	IC to Start of Other AE start date	None
20b	Cimzia	Gap only i.e. no evidence of Comparator or Cimzia dosing	Other AE during Gap	Gap	IC to EoS	None	None	None	IC to Start of Other AE start date	None

12 AMENDMENT(S) TO THE STATISTICAL ANALYSIS PLAN (SAP)

12.1 AMENDMENT 1

Rationale for the amendment

Amendment 1 of the SAP converts the original SAP dated 03Aug2009 from the PRA SAP template to the UCB SAP template, and includes new analyses as defined in amendment 3 of the protocol. In addition, the original TFL shells from 2009 have been converted from the PRA standard templates to UCB standard templates, and new shells have been included for the new analyses as defined in amendment 3 of the protocol.

12.2 AMENDMENT 2

Rationale for the amendment

Amendment 2 of the SAP adds new FDA analyses as requested in 13Dec2014 response letter. The SAP was also updated to the latest UCB SAP template.

12.3 AMENDMENT 3

Rationale for the amendment

Amendment 3 of the SAP is an update to account for the FDA feedback to stop enrollment and reduce the follow-up of patients from 10 years to 8 years. Additionally, several analyses were added in hopes to provide better interpretation of the data including updating the SMQs for MedDRA.

12.4 AMENDMENT 4

Rationale for the amendment

Amendment 4 of the SAP, from March 26, 2020, provides

- 1.) Specifications about the handling of erroneous patients entries. The rules for the handling of erroneous data are detailed in the Analysis Data Reviewers Guide, referenced in this SAP.
- 2.) A clarification of the censoring rules for time-to-event analyses, including sensitivity assessment.
- 3.) An update of important protocol deviations.

12.5 AMENDMENT 5

Rationale for the amendment

Amendment 5 of the SAP, dated September 1, 2020, provides an update to the censoring rules for the time-to-event analyses of Adverse Events of Interest. This now considers actual exposure until the occurrence of an Adverse Event of Interest, and makes the time at risk consistent with that of the exposure adjusted incidence analyses. There is also an update to state that analyses will be based on the FAS, and additionally on the ES.

STATISTICAL ANALYSIS PLAN SIGNATURE PAGE

This document has been reviewed and approved per the Review and Approval of Clinical Documents Standard Operating Procedures. Signatures indicate that the final version of the Statistical Analysis Plan (SAP) or amended SAP is released for execution.

REDACTED COPY
This document cannot be used to support any marketing authorization application and any extensions or variations thereof.

Approval Signatures

Name: C87075-SAP-Amend-5

Version: 1.0

Document Number: CLIN-000159691

